
In enfortumab vedotin monotherapy studies of urothelial carcinoma, serious adverse events of severe cutaneous adverse reactions were reported in 11 of 749 subjects (1.5%) and included dermatitis bullous (0.4%), drug eruption (0.4%), blister (0.1%), conjunctivitis (0.1%), SJS (0.1%), stomatitis (0.1%), and toxic skin eruption (0.1%).
 
Subjects should be advised to contact the Investigator immediately if they have signs and symptoms of skin reactions, oral mucosal and ocular abnormalities including mucositis or conjunctivitis. Starting in the first cycle and throughout treatment, closely monitor subjects for skin reactions. For mild to moderate skin reactions, consider appropriate treatment, such as topical corticosteroids and antihistamines as clinically indicated. For worsening Grade 2 rash or skin reactions, consider withholding enfortumab vedotin. For severe (Grade 3) rash or skin reactions or suspected SJS or TEN, withhold enfortumab vedotin and consider referral for specialized care. Permanently discontinue enfortumab vedotin in patients with confirmed SJS or TEN, or Grade 4 or recurrent Grade 3 skin reactions.
 
Deleted the following text:
 
In the phase 1 study (Study ASG 22CE 13-2), rash and similar dermatologic AEs were common among patients treated with enfortumab vedotin, and were seen more frequently at the highest dose. Although the exact etiology of dermatologic toxicities associated with enfortumab vedotin is unclear at this time, due to the expression of Neitin 4 in the skin, rash may be an on-target toxicity. The most common dermatological AEs reported in ASG 22CE 13-2 were drug eruption, rash, skin exfoliation, skin pigmentation disorder, and rash maculo papular. Most occurred during Cycle 1, and some were associated with pruritus. Almost all were mild, with the exception of two events of rash reported as Grade 3 in
	
--	--

	
the 1 mg/kg dose group. None required discontinuation of study drug and one event of Grade 1 papular rash at 1.25 mg/kg required a dose reduction. Mild rash related to enfortumab vedotin should be treated using local supportive care as needed. Topical corticosteroids have been used along with antihistamines for pruritus as needed. Grade 3 rash that is not limiting self care activities of daily living or associated with infection requiring systemic antibiotics does not require treatment interruption, provided symptoms are not severe and can be managed with supportive treatment.

--	--

Summary of Changes in Amendment 08

Sections	Change	Rationale
5.2.3 (Table 2)	
Dose modification recommendations for skin reactions related to enfortumab vedotin were modified as shown below, with additional formatting changes to accommodate the updated recommendations:
 
Any Grade:
 
For suspected Stevens-Johnson syndrome (SJS), suspected toxic epidermal necrolysis (TEN), or bullous lesions, immediately withhold enfortumab vedotin and refer the subject to a dermatologist/specialist for diagnosis and specialized care.
 
For confirmed SJS or TEN, permanently discontinue treatment.
 
If SJS or TEN is ruled out, see recommendations provided below for skin reactions.
 
Grade 2:
 
For worsening rash or skin reactions or skin reactions with concomitant fever, consider withholding enfortumab vedotin until toxicity is \leq Grade 1 or has returned to baseline, then resume treatment at the same dose level or consider dose reduction by 1 level. Consider referral of the subject to a dermatologist/specialist for diagnosis and specialized care. See also Section 5.10.5 for recommended management of rash.
 
Grade 3:
 
For Grade 3 rash or skin reactions withhold enfortumab vedotin until toxicity is \leq Grade 1 or has returned to baseline, then resume treatment at the same dose level or consider dose reduction by 1 level. Consider referral of the subject to a dermatologist/specialist for diagnosis and specialized care. See also Section 5.2.3 for recommended management of rash.
 
For suspected Stevens Johnson Syndrome (SJS) or suspected toxic epidermal necrolysis (TEN) withhold enfortumab vedotin. Consider referral of the subject to a dermatologist/specialist for diagnosis and specialized care.
	Guidance modified to clarify dose modification recommendations for bullous lesions and certain Grade 2 skin reactions.

	Subjects who have confirmed SJS or recurrent Grade 3 rash events should have therapy permanently discontinued.	
5.4.3	
Subjects should be informed that rash and severe skin reactions have occurred after administration of enfortumab vedotin and advised to contact the Investigator immediately if they have signs and symptoms of skin reactions, oral mucosal and ocular abnormalities including mucositis or conjunctivitis.
 
Starting in the first cycle and throughout treatment, closely monitor subjects for skin reactions. For mild to moderate skin reactions, consider appropriate treatment, such as topical corticosteroids and antihistamines as clinically indicated. For recommendations regarding dose modifications for skin reactions due to enfortumab vedotin, refer to Section 5.2.3. For worsening Grade 2 rash or skin reactions, consider withholding enfortumab vedotin. For severe (Grade 3) rash or skin reactions or suspected SJS or TEN, withhold enfortumab vedotin and consider referral for specialized care. Permanently discontinue enfortumab vedotin in patients with confirmed SJS or TEN, or Grade 4 or recurrent Grade 3 skin reactions.
	For clarity, the section on management of rash was updated to refer directly to dose modification recommendations in Section 5.2.3, rather than repeat the same information in this section.

Summary of Changes in Amendment 09

Sections	Change	Rationale
5.2.3 (Table 2)	
Dose modification recommendations for pneumonitis/ILD related to enfortumab vedotin were added as shown below, with additional formatting changes to accommodate the updated recommendations:
 
Grade 2: Continue at same dose level, except in the event of Grade 2 neuropathy, corneal AEs, or pneumonitis/ILD.
 
For Grade 2 pneumonitis/ILD, withhold dose until \leq Grade 1, then resume at the same dose level or consider dose reduction by 1 dose level.
 
Grade 3: For Grade 3 pneumonitis/ILD, permanently discontinue treatment.
 
Grade 4: For Grade 4 pneumonitis/ILD, permanently discontinue treatment.
	Severe, life-threatening, or fatal pneumonitis/interstitial lung disease has occurred in patients receiving enfortumab vedotin and recommendations regarding management of and dose modifications for pneumonitis/interstitial lung disease due to enfortumab vedotin were added to the protocol.
5.4.4	
Added new Section 5.4.4 for management of pneumonitis/ILD related to enfortumab vedotin as shown below:
 
5.4.4 Management of Pneumonitis/ILD Related to Enfortumab Vedotin
 
Severe, life-threatening or fatal pneumonitis/interstitial lung disease (ILD) have occurred in patients receiving enfortumab vedotin. Monitor patients for signs and symptoms indicative of pneumonitis/ILD such as hypoxia, cough, dyspnea or interstitial infiltrates on radiologic exams. For recommendations regarding dose modifications for pneumonitis/ILD due to enfortumab vedotin, refer to Section 5.2.3.
	The section on management of adverse reactions was updated to include new section on management of pneumonitis/ILD.

1 INTRODUCTION

This document outlines the statistical methods to be implemented within the scope of Protocol SGN22E-001, entitled “A single-arm, open-label, multicenter study of enfortumab vedotin (ASG-22CE) for treatment of patients with locally advanced or metastatic urothelial cancer who previously received immune checkpoint inhibitor (CPI) therapy”. Results of the proposed analyses will become the basis of the clinical study report (CSR) for this protocol.

The purpose of this plan is to provide specific guidelines from which the analysis will proceed. All planned analyses specified in this document will be performed. Any changes to this plan, in the form of “post hoc” or “data driven” analyses will be identified as such in the final CSR. Any changes will either be reflected in amendments to this plan before the database lock or specifically documented in the CSR.

2 STUDY OBJECTIVES

2.1 Primary Objectives

- To determine the antitumor activity of single-agent enfortumab vedotin as measured by confirmed objective response rate (ORR) in patients with locally advanced or metastatic urothelial cancer who have previously received systemic therapy with a CPI and either received platinum-containing chemotherapy or are platinum-naïve and cisplatin-ineligible

2.2 Secondary Objectives

- To assess duration of response (DOR)
- To assess disease control rate (DCR)
- To assess progression-free survival (PFS)
- To assess overall survival (OS)
- To assess the safety and tolerability of enfortumab vedotin
- To assess the pharmacokinetics (PK) of enfortumab vedotin
- To assess the incidence of antitherapeutic antibodies (ATA)

2.3 Additional Objectives

- To explore potential correlations between biomarkers and clinical outcomes
- To evaluate the treatment effect of enfortumab vedotin on quality of life (QoL)

3 STUDY ENDPOINTS

3.1 Primary Endpoint

The primary efficacy endpoint of this study is ORR (confirmed complete response [CR] or partial response [PR] per Response Evaluation Criteria in Solid Tumors [RECIST] Version 1.1) as determined by an independent review facility (IRF)

3.2 Secondary Endpoints

- DOR (confirmed CR or PR) per IRF
- DCR₁₆ (DCR [CR, PR or stable disease (SD)] at 16 weeks) per IRF
- PFS per IRF
- ORR per investigator assessment
- DOR per investigator assessment
- DCR₁₆ per investigator assessment
- PFS per investigator assessment
- OS
- Type, incidence, severity, seriousness, and relatedness of adverse events (AEs)
- Laboratory abnormalities
- Selected plasma or serum PK parameters of enfortumab vedotin and monomethyl auristatin E (MMAE)
- Incidence of ATA to enfortumab vedotin

3.3 Additional Endpoints

- Biomarkers of biological and clinical activity, including Nectin-4 expression
- Patient reported outcomes (PRO) per the EORTC Quality of Life Questionnaire (QLQ-C30)
- PRO per EuroQol 5-dimensions (EQ-5D), including health utility values, and visual analog scale

4 STUDY DESIGN

This is a single-arm, open-label, multicenter trial designed to assess the efficacy and safety of enfortumab vedotin as a single agent in locally advanced or metastatic urothelial cancer subjects who have previously received systemic therapy with a CPI. Subjects must also either have received prior treatment with platinum-containing chemotherapy (Cohort 1) or received no prior platinum-containing or other chemotherapy and are ineligible for treatment with

cisplatin (Cohort 2). Subjects must have progressive disease (PD) during or following their most recent therapy. There are no limits for prior lines of therapy, including taxanes.

Enfortumab vedotin at a dose of 1.25 mg/kg will be administered as an intravenous infusion on Days 1, 8, and 15 of each 28-day cycle. Subjects will continue to receive study treatment until disease progression, unacceptable toxicity, investigator decision, consent withdrawal, start of subsequent anticancer therapy, pregnancy, or study termination by the sponsor.

Subjects who discontinue study treatment for reasons other than disease progression per RECIST v1.1 or start of subsequent anticancer therapy will continue to have response assessments, Eastern Cooperative Oncology Group (ECOG) performance status, and physical exams every 8 weeks (± 1 week). After 1 year on study, the frequency of follow-up exams including response assessments will be reduced to every 12 weeks (± 1 week). Subjects who have progressed or begun subsequent anticancer therapy will be contacted every 8 weeks (± 1 week) up to 1 year on study, and every 12 weeks (± 1 week) thereafter to obtain information on subsequent anticancer therapy, and survival status until death, study closure, withdrawal of consent, or subject is lost to follow-up, whichever occurs first (see Figure 1). The study will be closed 5 years after enrollment of the last subject, or when no subjects remain in long-term follow-up, whichever occurs first. Additionally, the sponsor may terminate the study at any time.

Measures of anticancer activity will be assessed by radiographic tumor imaging at protocol-specified timepoints. Tumor response will be assessed locally and centrally by an IRF according to RECIST v1.1 (Eisenhauer 2009). Clinical response of CR, PR, SD, or PD will be determined at each assessment. Responses (CR or PR) will be confirmed with repeat scans at least 4 weeks after first documentation of response. Tumor assessments will continue until the subject has radiologically-confirmed disease progression per RECIST v1.1 by the investigator, initiates a new anticancer therapy, dies, withdraws consent, or the study closes, whichever comes first.

Safety assessments will be based on the information collected through the safety surveillance process and will include the data from recorded AEs including serious adverse events (SAEs), recording of concomitant medication, medical history, physical examination findings, and laboratory tests.

[figure not shown]
Approximately 200 subjects will be enrolled in this study, including approximately 100 or more platinum-treated subjects (Cohort 1) and up to approximately 100 platinum-naïve and cisplatin-ineligible subjects (Cohort 2).

On a periodic basis, approximately every 3 months until all treated subjects in Cohort 1 have had the opportunity to be followed for at least 6 months and at a frequency considered adequate based on the rate of enrollment to Cohort 2 thereafter, an independent data monitoring committee (IDMC) will monitor the safety of subjects participating in this trial. The IDMC will be guided by an independent charter and will be responsible for evaluating the results of safety analyses and will make recommendations to the sponsor. The IDMC may also request efficacy data, if needed, to evaluate risk/benefit before making

recommendations. The IDMC will make recommendations to either continue the study unchanged, modify the study, or discontinue the study. The final decision to act on the IDMC recommendations will be made by the sponsor.

An ongoing real-time review of subject safety and SAEs will also be conducted by the sponsor's Drug Safety Department.

Figure 1 Study Schema

^a There are 2 cohorts of CPI-treated patients in the study: Cohort 1) platinum-treated patients, and Cohort 2) platinum-naïve/cisplatin-ineligible patients.

^b After 1 year on study, the frequency of response assessments will be reduced to every 12 weeks (±1 week).

A detailed study assessment schedule can be found in the protocol.

5 ANALYSIS SETS

5.1 Full Analysis Set

The full analysis set will include all subjects who are enrolled in the study and receive any amount of enfortumab vedotin.

The full analysis set will be used as the primary analysis set for efficacy endpoints. Subject demographics and baseline disease characteristics will be summarized based on the full analysis set.

5.2 Safety Analysis Set

The safety analysis set will include all subjects who receive any amount of enfortumab vedotin, and thus is equivalent to the full analysis set defined in this protocol. The safety analysis set will be used for all safety analyses.

5.3 Efficacy Evaluable Set

The efficacy evaluable set will include all subjects in the full analysis set who started treatment with enfortumab vedotin at least 8 months before the analysis data cutoff. The efficacy evaluable set will be used for the additional analyses of efficacy endpoints at the

time of the Cohort 2 interim analyses to allow adequate follow up for a stable estimate of ORR and DOR.

5.4 Pharmacokinetics (PK) Analysis Set

The PK analysis set will include all subjects who received enfortumab vedotin and from whom at least one blood sample was collected and assayed for enfortumab vedotin, MMAE or TAb concentration. Corresponding records of the time of dosing and sample collection must also be available for all enfortumab vedotin, MMAE and TAb concentration data. The PK analysis set will be used for PK analyses.

6 STATISTICAL CONSIDERATIONS

6.1 General Principles

In general, all analyses will be performed separately for each cohort and the 2 cohorts combined, unless otherwise specified. Descriptive statistics will be presented that include the number of observations, mean, median, standard deviation, minimum and maximum for continuous variables, and the number and percentages (of non-missing) per category for categorical variables.

Unless otherwise specified, confidence intervals (CIs) will be calculated at two-sided 95% level.

The two-sided 95% exact CI using the Clopper-Pearson method will be calculated for the response rates where applicable (e.g., ORR) (Clopper 1934).

For time-to-event endpoints, the median survival time will be estimated using the Kaplan-Meier method; the associated 95% CI will be calculated based on the complementary log-log transformation (Collett 1994).

Any analysis not described in this plan will be considered exploratory, and will be documented in the CSR as a post hoc analysis.

To comply with regulatory electronic submission guidelines, listings of all clinical data will be submitted as electronic data sets. To facilitate data review for the study report, only pertinent data listings will be created and attached to Section 16 of the study report.

All statistical Tables, Listings and Figures will be produced using SAS[®], version 9.3 or higher. Sample size calculations were performed using EAST[®], version 6.0. Other statistical software, if used, will be described in the CSR.

6.2 Determination of Sample Size

The study is designed to estimate the confirmed ORR in the full analysis set and to detect an improvement in the ORR compared with a historical 10% response rate.

The primary efficacy hypothesis is

$$H_0: ORR \leq 10\% \text{ vs. } H_a: ORR > 10\%$$

Approximately 200 subjects will be enrolled to ensure collection of sufficient efficacy and safety data, including approximately 100 or more platinum-treated subjects (Cohort 1) and up to approximately 100 platinum-naïve and cisplatin-ineligible subjects (Cohort 2). Using the estimate of approximately 100 subjects in Cohort 1, the study will have 98% power to detect a 15% increase in ORR from 10% to 25%, and 81% power to detect a 10% increase in ORR from 10% to 20%, at one-sided significance level of 0.025, based on exact methods using EAST®, Version 6.0, by Cytel Inc.

The confirmed ORR and 95% exact CI for subjects in Cohort 2 will be summarized at 4 timepoints:

- 1) at the time of the primary analysis of Cohort 1 (i.e., after all subjects in Cohort 1 have had the opportunity to be followed for at least 6 months),
- 2) when approximately 50 subjects in Cohort 2 have had the opportunity to be followed for approximately 8 months from the first dose of enfortumab vedotin,
- 3) when approximately 70 subjects in Cohort 2 have had the opportunity to be followed for approximately 8 months from the first dose of enfortumab vedotin, and
- 4) when all subjects in Cohort 2 have had the opportunity to be followed for approximately 8 months from the first dose of enfortumab vedotin.

For illustration purpose, assuming the observed ORR in Cohort 2 is 30%, the 95% exact CIs of ORR based on the expected number of subjects at each analysis timepoint are summarized below:

Number of Subjects	95% Exact CI
N=20	(12%, 54%)
N=50	(18%, 45%)
N=70	(20%, 42%)
N=100	(21%, 40%)

Sample Size for IDMC Assessment of Slit Lamp Examination

Slit lamp examinations will be conducted on at least the first 60 enrolled subjects (from Cohorts 1 and/or 2) on Cycle 2 Day 22 (± 1 week) and Cycle 6 Day 22 (± 1 week). If treatment-emergent corneal events are observed in <15% of the first 60 enrolled subjects and if the events are generally low grade or asymptomatic, the IDMC may make a recommendation to cease Cycle 2 Day 22 and/or Cycle 6 Day 22 slit lamp exams for the remaining subjects if warranted based on review of the cumulative ocular safety data. Based on the results from the Phase 1 study (Study ASG-22CE-13-2), as of the data cutoff date of 14 November 2016, there were 3 subjects who reported experiencing corneal adverse events out of 33 subjects (9%) on 1.25 kg/mg of enfortumab vedotin. Assuming an event rate of 9%,

with a sample size of 60, the probability of observing >3 events (5%) is 80.0% and the probability of observing <9 events (15%) is 91.2%. If the event rate is higher, the probability of observing <9 events is decreased. For example, if the event rate is 20%, the probability of observing <9 events is decreased to 12.7%.

6.3 Randomization and Blinding

This is a single-arm, open-label study. No randomization or blinding will be used.

6.4 Data Transformations and Derivations

6.4.1 General

Reported age in years will be used; if not available, age at informed consent in years will be calculated with the SAS® INTCK function (with method specified as “continuous”) using informed consent date and birth date.

Study Day will be calculated as (Date – First Dose Date + 1) for dates on or after the first dose date. The date of first dose will be Study Day 1. For dates prior to the first dose date, Study Day will be calculated as (Date – First Dose Date). For example, the date before the first dose date will be Study Day -1.

Other time variables based on two dates, e.g., Start Date and End Date, will be calculated as (End Date – Start Date + 1) (in days) unless otherwise specified in the planned analysis section.

The following unit conversion will be implemented unless otherwise specified:

$$\text{Months} = \text{Days} / 30.4375$$

$$\text{Years} = \text{Days} / 365.25$$

Unless otherwise specified, baseline values used in all analyses will be the most recent non-missing measurement prior to the first dose of study drug.

6.4.2 Best Overall Response

The subject’s best overall response per IRF will be the best demonstrated response to date that has been confirmed, when confirmation is required (i.e. for PR and CR). Response after the start of subsequent anticancer therapy will not be included in the derivation of best overall response. The subject’s best overall response will be used in determining the ORR per IRF.

A response (CR or PR) will be considered confirmed if the subsequent response assessment (at least 4 weeks after the initial response) still shows response (CR or PR). A subject will have a best response of SD if there is at least one SD assessment (or better) ≥ 6 weeks after the start of treatment and the subject does not qualify for confirmed CR or PR. RECIST v1.1 outlines scenarios for best overall responses when confirmation of CR and PR is required.

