9.2 Study Endpoint Definitions

9.2.1 Objective Response Rate

The primary endpoint of this study is the confirmed ORR per IRF. The ORR is defined as the proportion of patients with confirmed CR or PR according to RECIST Version 1.1 (see [Appendix D](#)) ([Eisenhauer 2009](#)). Patients who do not have at least 2 (initial response and confirmation scan) post-baseline response assessments as described in [Section 7.2](#) of the protocol will be counted as non-responders.

In addition, ORR per investigator will be analyzed as a secondary endpoint.

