APPENDIX D: RECIST CRITERIA SUMMARY (VERSION 1.1)

Response Evaluation Criteria in Solid Tumors	
Term	Definition
Complete response (CR)	Disappearance of all target lesions. Any pathological lymph nodes must have reduction in short axis to <10 mm.
Partial response (PR)	A $\geq 30\%$ decrease in the sum of diameters of target lesions, taking as reference the baseline sum diameters.
Progressive disease (PD)	At least a 20% increase in the sum of diameters of target lesions, taking as reference the smallest sum on study (this includes the baseline sum if that is the smallest on study). In addition to the relative increase of 20%, the sum must also demonstrate an absolute increase of at least 0.5 cm. The appearance of one or more new lesions is also considered progression.
Stable disease (SD)	Neither sufficient shrinkage to qualify for PR nor sufficient increase to qualify for PD, taking as reference the smallest sum diameters while on study.
Measurable lesion	Must be accurately measured in at least one dimension (longest diameter in the plane of measurement is to be recorded) with a minimum size of 10 mm by CT scan (CT slice thickness no greater than 5 mm). A lymph node must be ≥ 15 mm in short axis when assessed by CT scan to be considered measurable.

From RECIST Version 1.1 ([Eisenhauer 2009](#))

A response (CR or PR) will be considered confirmed if the following disease assessment (at least 4 weeks after the initial response) still shows response (CR or PR). In cases where the initial response is followed by SD, it will be considered as confirmed if the SD is later followed by PR or CR. For example, if a patient had PR in week 8, SD in week 12, and PR in week 16, this PR will be considered as confirmed.

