6.4.3 Response Assessment Dates

At each response assessment time point, scans to evaluate target and non-target lesions can be performed on multiple dates. If the time point response is CR or PR, then the latest date of all radiologic scans at the given response assessment visit will be the date of response. If the time point response is SD, then the earliest date of all radiologic scans at the given response assessment visit will be the date of SD. If the time point response is PD, then the earliest date that PD has been documented will be the date of PD, i.e. the earliest of:

- Date of target lesion assessments when the target lesion response is PD
- Date of non-target lesion assessments when the lesion status is unequivocal progression
- Date of documenting new lesions

For subjects whose best overall response is a confirmed CR or PR, the date of objective response will be the date of initial documentation of response (i.e., CR or PR that is subsequently confirmed).

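### SAP 6.4.2 omits the protocol's rule that a response interrupted by stable disease can still be confirmed

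*SAP*

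**What the plan says.** **Protocol.** Section 9.2.1 defines the primary endpoint as the "proportion of patients with confirmed CR or PR according to RECIST Version 1.1" and refers the reader to Appendix D. Section 9.3.5.1 repeats this. Appendix D gives two routes to confirmation. The first is that the following assessment, four or more weeks on, still shows response. The second covers an intervening SD: "where the initial response is followed by SD, it will be considered as confirmed if the SD is later followed by PR or CR". It adds a worked example: "if a patient had PR in week 8, SD in week 12, and PR in week 16, this PR will be considered as confirmed".

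**SAP.** Section 6.4.2 derives the best overall response that feeds ORR per IRF. It gives the first route, under which a response is "considered confirmed if the subsequent response assessment (at least 4 weeks after the initial response) still shows response (CR or PR"). It does not give the second route or the example, and does not cite Appendix D. Best response is SD when there is an SD or better at six weeks or later and "the subject does not qualify for confirmed CR or PR". The paragraph ends with a general pointer: "RECIST v1.1 outlines scenarios for best overall responses when confirmation of CR and PR is required".

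**Elsewhere in the SAP.** Section 4 says responses "will be confirmed with repeat scans at least 4 weeks after first documentation of response". Section 6.4.3 says that, for confirmed responders, "the date of objective response will be the date of initial documentation of response", meaning a response that is later confirmed. Sections 6.5 and 7.5.1 treat subjects with fewer than two post-baseline assessments as non-responders. Section 9.1 declares no changes from the original protocol.

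**The concern.** SAP 6.4.2 is the text from which the primary endpoint will be programmed. It carries over the first half of the protocol's confirmation rule almost unchanged and leaves out the second half. A programmer who codes it as written will classify the protocol's own example differently from the protocol.

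The pattern is a practical one. Protocol 7.2 illustrates the scan schedule with a response at week 8, a confirmatory scan at week 12 and the next assessment at week 16, which is the timing in the Appendix D example. At stake are who counts as a responder, the date on which some responses begin, and who enters the responder-only summaries of duration of response and time to response.

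**Working it through.** **1. The plan's design figures.** Inputs from SAP 6.2: N=100, null ORR 10%, one-sided 0.025, exact test. The smallest r with P(X ≥ r | 100, 0.10) ≤ 0.025 is r=17 (exact level 0.0206; r=16 gives 0.0399). Power is P(X ≥ 17) = 97.9% at ORR 25% and 80.8% at 20%, matching the stated 98% and 81%. The illustrative Clopper-Pearson intervals also reproduce: 6/20 gives 11.9-54.3%, 15/50 gives 17.9-44.6%, 21/70 gives 19.6-42.1% and 30/100 gives 21.2-40.0%. Adding the missing rule changes none of these figures.

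**2. The two rules applied to response sequences.**

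| Sequence | SAP 6.4.2 coded literally | Appendix D |
|---|---|---|
| PR wk 8, PR wk 12 | confirmed | confirmed |
| PR wk 8, SD wk 12, PR wk 16 | not confirmed | confirmed |
| PR wk 8, SD wk 12, PR wk 16, PD wk 24 | not confirmed | confirmed |
| PR wk 8, SD wk 12, PR wk 16, PR wk 20 | confirmed through the wk 16 PR | confirmed from the wk 8 PR |

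In rows 2 and 3 the patient becomes a non-responder with best response SD. The two-assessment requirement in SAP 6.5 and 7.5.1 does not settle the matter, because these patients have three or more assessments.

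**3. Response date in the last row.** If the date follows the PR that met the literal rule, it moves from week 8 to week 16: 8 × 7 = 56 days, or 56/30.4375 = 1.84 months. If SAP 6.4.3 is read as pointing to the first PR, it does not move. The text allows both.

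**4. Size for ORR.** Each patient who becomes a non-responder lowers ORR by 100/N points: 5.0 at N=20, 2.0 at N=50, 1.4 at N=70 and 1.0 at N=100. At N=100, going from 30 to 29 responders changes the interval from 21.2-40.0% to 20.4-38.9%.

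**5. The 10% benchmark.** The lower limit is 9.43% at 16/100 and 10.23% at 17/100. Let X be the number of responders under Appendix D and k the number lost under literal coding. The lower limit falls from above 10% to below it only if 17 ≤ X ≤ 16+k. The documents do not give k; I assume 1 to 3.

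| True ORR | k=1 | k=2 | k=3 |
|---|---|---|---|
| 20% | 7.9% | 17.0% | 26.8% |
| 25% | 1.7% | 4.2% | 7.8% |
| 30% | 0.12% | 0.36% | 0.79% |

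For a given number of affected patients these are upper bounds, since those whose second response is later confirmed remain responders. For scale, Protocol 1.6 reports a phase 1 confirmed ORR of 31% (17/55) in CPI-treated patients at the study dose.

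**6. Duration of response and time to response.** SAP 7.5.3 and 7.5.1 calculate both in confirmed responders only. The patient in row 3 has a response of about 16 weeks (week 8 to week 24) under Appendix D and drops out of both summaries under literal coding. If most other responses last longer than 16 weeks, the median duration can rise. Dropping a patient who responded late can shorten the median time to response. Where a patient stays in with a later date (step 3), the shift goes the other way. The net direction is not determined.

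**The case against.** The best defence is that the SAP does not exclude the Appendix D rule. Section 6.4.2 states a sufficient condition, not a necessary one, and sends the reader to RECIST v1.1 for confirmation scenarios. Section 4 asks only for repeat scans four or more weeks after first response. The protocol's endpoint definition cites Appendix D, and the SAP declares no departure. This stands as a reason not to call the documents contradictory. It does not remove the gap. The word for *still* in the SAP sentence, and its close parallel with Appendix D's first route, favour the next-assessment reading. The RECIST pointer is general and does not state the rule. No other SAP section supplies it.

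A reader might infer that the confirmation rule covers the IRF only, leaving the investigator derivation without one. The text does not support that. The opening paragraph of 6.4.2 names the IRF, but the confirmation sentence is unqualified. Protocol 9.3.5.2 calls for confirmed ORR per investigator, and SAP 7.5.3 analyses duration of response per investigator in the same way as per IRF.

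It is also fair to object that the count of affected patients is assumed. At a true ORR of 20%, k=3 with 17 to 19 responders means 3/19 to 3/17, or 16-18%, of responders depend on this route. That is an extreme case, and the 26.8% should be read as such.

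**Conclusion.** The point holds as a minor inconsistency in the derivation of the primary endpoint. Followed literally, SAP 6.4.2 misclassifies the protocol's own example unless a later scan confirms the second PR, and in that case the response date may move by 8 weeks.

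For ORR the direction is certain: literal coding can only lower it, by 1.0 point per affected patient at N=100. A reader might go further and call literal coding conservative throughout, always delaying response and shortening its duration. That does not follow for the cohort summaries, because removing a patient from a responder-only analysis can move a median either way.

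A reader might also infer that the comparison with 10% is at risk. With an assumed 1 to 3 affected patients, the chance of a changed conclusion is at most 7.8% at an ORR of 25% and below 1% at 30%, so it is unlikely in that range. The design power figures are sound and unaffected.

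**What to change.** Add the intervening-SD rule from Appendix D to SAP 6.4.2, or an explicit cross-reference to Appendix D. State in the same sentence that the rule serves both the IRF and the investigator derivations. The response date then follows from SAP 6.4.3 unchanged: in the example the week 8 PR is the confirmed response, so it sets the date.

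The cost is one SAP sentence. No new data, additional output, sensitivity analysis or protocol amendment is needed.
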